- **Inflammation** (CRP, WBC, Th-1/TH-2 cytokines)

Archer et al found that arginine down-regulates inflammatory pathways (19) in the sickle cell transgenic mouse model. In particular C-reactive protein (CRP) and interleukin-6 were decreased in mice fed a high protein diet. CRP and a panel of inflammatory cytokines will be evaluated pre and post therapy to determine if this observation translates to human SCD.

- **Hemolysis** (LDH, Hb, retic count, bilirubin, cell-free Hb).

Hemolysis contributes significantly to an altered arginine metabolome in SCD (2, 29, 94-96) and will be evaluated. **Whether arginine has any impact hemolytic rate is unknown, however the degree of hemolysis in individual patients presenting with VOE may impact the severity of their acute arginine deficiency and response to therapy.** Past studies demonstrating an effect of arginine therapy on erythrocyte GSH levels could impact degree of hemolysis. Our preliminary data demonstrated a trend towards lower retic count in the arginine arm compared to placebo (1), and should be followed.

- **Exhaled nitric oxide**

Exhaled nitric oxide is a non-invasive procedure that is considered to be an indirect measurement of airway inflammation. It is also impacted by supplemental arginine. Subjects will be instructed to take in a deep breath and blow air out at a constant pressure as directed by personnel through a standardized method. One measurement will be taken and recorded at Day 0 and daily during hospitalization.

- **Cerebral and Muscle Blood Flow**

Subjects will have a sticky sensor gently secured to the forehead and/or arm or leg to look at blood flowing to the brain or painful arm/leg and blood flow to the arm or leg that does not hurt before study drug is delivered, and then after study drug is delivered for up to 8 hours on the first day, and then for 5-10 minutes daily (20 minutes maximum). A blood pressure sensor will be secured to the subject's upper arm and fore finger during this time.

- **Mitochondrial function**

Mitochondrial dysfunction in the platelets of SCD patients. In a pilot study, we isolated platelets from the blood of adult SCD patients & healthy African American volunteers. Comprehensive analysis of mitochondrial function demonstrated that SCD patients manifested mitochondrial dysfunction characterized by decreased complex V activity compared to healthy African American subjects (Fig 8). A decrease in complex V activity, the ATPase required for ATP generation by oxidative phosphorylation, potentially results in increased mitochondrial reactive oxygen species production (through electron buildup in complexes I-IV) and decreased ATP generation. Consistent with this, we have measured increased mitochondrial ROS generation in SCD platelets compared to healthy controls (Fig 9A-C).

Mitochondrial dysfunction in SCD patients can be mimicked by oxidative stress. To determine whether oxidative stress causes mitochondrial dysfunction in mitochondria of SCD patients, healthy human platelets were exposed to free hemoglobin in vitro, a generator of oxidants through auto-oxidation of heme. Free hemoglobin (100uM) caused a decrease in mitochondrial complex V activity, which was prevented when an antioxidant (TEMPOL; 250uM) was included in the incubation (Figure 10).

Collectively, these data suggest that platelets from SCD patients manifest mitochondrial dysfunction that is potentially propagated by oxidative stress. Information on ADMA and mitochondrial dysfunction will also provide insight into these 2 overlapping mechanisms.

***Blood volume obtained from children with SCD may sometimes vary due to difficult IV access. Studies run for research labs will be prioritized to arginine metabolome. Additional secondary tests will be analyzed based on available blood sample. Use of discarded samples saved up to 72 hours will also be used to run research specified labs only if needed.**

PARTICIPANT SELECTION

The research coordinator/study team will review the ED track board and daily admission logs, and approach patients for enrollment who meet the following inclusion criteria:

Inclusion Criteria

- Established diagnosis of sickle cell disease (all SCD genotypes)
- Age 3-21 years of age
- Pain requiring medical care in an acute care setting (ED, hospital ward, day hospital, clinic)

not attributable to non-sickle cell causes, that is moderate-to-severe treated with parenteral opioids

Exclusion Criteria

- Decision to discharge home from acute care setting.
- Hemoglobin less than 5 gm/dL or immediate need for red cell transfusion anticipated within the next 12 hours.
- Hepatic dysfunction: SGPT (ALT) > 3X upper value
- Renal dysfunction: Creatinine >1.0
- Mental status or neurological changes
- Acute stroke or clinical concern for stroke
- Pregnancy
- Allergy to arginine
- Two (2) or more ED visits within the last 7 days prior to CURRENT ED visit
- Hospital discharge < 14 days prior to presentation to ER.
- Previous randomization in this arginine RCT (patient consented and screen failed before receiving study drug or placebo remains eligible for future participation).
- Patient refusal
- Use of inhaled nitric oxide, sildenafil or arginine within the last month
- Acidosis with CO₂ ≤ 16
- Hypotension requiring treatment with clinical intervention
- Not an appropriate candidate in the investigator's judgement
- Newly started on HU for < 3 months
- PICU admission from the emergency department

Patients will be given or sent electronically a standard consent form prior to study enrollment approved by the institutional review board (IRB). This consent form will provide a brief summary of the study protocol and will provide families with contact information for the principle investigator and IRB personnel should they have any questions/concerns about the study. Both informed parental consent and patient assent, where appropriate, will be obtained electronically, and when appropriate a paper consent can be obtained. A copy of the consent and assent, where appropriate, will be placed in the patient's medical chart. If a copy of the consent form is sent electronically to a patient, this will be sent either via REDCap or via encrypted email, as such the patient's electronic mailing address will be captured.

A study binder will be kept by the research coordinator/enrollers that will record the names and unique identification code of each patient approached for enrollment in an enrollment log. The names and demographic information (age, gender, Hb-genotype) of those who were approached and decline enrollment and the reason for declining (if known) will be recorded as approached/not enrolled. Age, gender and Hb-genotype information on patients screened by the study team/coordinator but found to be not eligible will also be collected. All study binders will be kept in a locked cabinet in the research office of the PED or Aflac coordinators and electronic files with any private health information (PHI) will be kept in a password protected CHOA supported division sharepoint site that is backed up nightly. Only members of the study team will have access to the study folder.

Randomization and Arginine/Placebo Administration

Arginine/Placebo will be administered in a blinded fashion. Using randomization lists prepared by the

research pharmacist, the research pharmacist at Egleston Children's Hospital will perform a block randomization for all CHOA sites, and study drug will be allocated to the patient TID until discharge. **Randomization will be stratified for hydroxyurea use to insure an equal number of patients on HU in all arms to minimize this as a potential confounder.** The patient, nurses, and physicians caring for the patient will be blinded as to which medication the patient is receiving.

Once written informed consent is obtained, and eligibility is confirmed by study staff, children and adolescents age 3-21 years will be randomized to one of following three study arms:

- 1) Standard L-arginine dose (100mg/kg IV TID)
- 2) One-time L-arginine loading dose (200mg/kg IV) plus the standard dose (100mg/kg IV TID)
- 3) Placebo (normal saline 1-2 ml/kg IV TID)

Upon enrolment, the patient's medical record is reviewed for CMP and creatinine testing in the past month in the past 12 months.

- If there are no measurements within the past 12 months or if either SGPT/ALT or creatinine were elevated in the past 12 months (meeting exclusion criteria), the current CMP results must be reviewed prior to dose administration. (Patient may be randomized; however, delivery of study drug should be held until CMP results are reviewed and no exclusion criteria are noted).
- If CMP and creatinine levels were normal enough to not meet exclusion criteria in the past 12 months, the patient can receive the first dose of study drug and the CMP and creatinine labs reviewed when available.
- Patients with a CMP after randomization that meet exclusion criteria will have study drug stopped for toxicity monitoring. With an intention-to-treat analysis, these patients will remain on study. Blood analysis and exhaled NO_x measurements will continue per protocol, but arginine/placebo supplementation will be terminated.

Administration of Analgesics to Study Patients

Patient Controlled Analgesia (PCA) devices will be used in admitted patients whenever possible according to standard practice at CHOA. Intravenous ketorolac, oral NSAIDS and oral opioids with acetaminophen may be used in addition to parenteral opioids. Intranasal fentanyl may be administered at presentation in the ED per protocol. Dosing of the PCA will follow a standard protocol of pain management established by the Aflac sickle cell center.

Monitoring During Study

Patients will be identified from the over 1400 ED SCD patient visits/year for VOE in children followed by the staff at the Aflac Sickle Cell Center of CHOA/Emory University School of Medical. They will be examined daily by the clinical team and will undergo routine vital signs including blood pressure per clinical protocol. A chart review will be performed, and pertinent data extracted. A pain score will be obtained and recorded daily (at least 3 times a day, once per shift) and at time of discharge. Standard of care pain scores will be utilized. A symptom questionnaire to assess for potential side effects of arginine will be completed daily by the study coordinator (see appendix). Information for the symptom's questionnaire evaluating for potential adverse events should be obtained by direct questioning of the patient/family in addition to the medical record. Use of parenteral narcotics will be documented every shift by nursing staff per standard protocol and will include narcotics delivered by the PCA device as well as any additional intravenous, intranasal and/or oral opioids used. Data on total daily opioid use will be collected by study team coordinator.

Laboratory monitoring will be undertaken according to the schedule below:

	DAY 0	DAY 1	Day 7/Discharge*
CBC with retic count (SOC)	X	X	X
Comprehensive metabolic panel	X	X	X
Urinalysis for protein (urine to Brown lab)	X	X	X
BHCG (girls > 12 yrs)	X		
RESEARCH LABS	X		X
See Specific Aim 3			
Arginine Metabolome	X	X	X

Total research Blood draw/day < 20 cc (less than 2 tablespoons)

*Day 0 pre-study drug delivery and Day 1 is the first day >12 hours after study drug initiation. If routine daily labs occur within < 12 hours of the first study drug dose, day 1 labs may be rescheduled to the following day. *Discharge bloodwork will be obtained on Day 7 of arginine therapy for prolonged admissions AND day of discharge. Day 7 is the day that the last dose # 21 will be given for patients who have not yet been discharged. Discharge labs may be obtained with routine daily blood draw whenever possible and may be drawn on days when the research and clinical team suspect the patient may be discharged, to avoid multiple venipuncture. In the event the patient is not discharged on that date, discharge labs should be drawn again prior to discharge. Tests may be run on discarded samples saved up to 72 hours if needed.*

Toxicity Monitoring/ Study Drug Stopping Rules

Patients will be removed from the study if they meet the following criteria:

- 1) Neurological dysfunction or development of stroke while on protocol
- 2) Increase in SGPT to > 6X ULN value
- 3) Increase in creatinine to >3X value at study entry or >2.0
- 4) Allergic reaction to study medication
- 5) Patient's request
- 6) Acidosis with CO₂ ≤ 16
- 7) Hypotension requiring treatment with clinical intervention
- 8) Concern by study team and sickle cell clinical team that a serious adverse event is related to study drug

Data from patients removed from the study will be collected and analyzed for potential side effects or toxicities of arginine. Blood analysis and exhaled NO_x measurements will continue per protocol, but arginine/placebo supplementation will be terminated. Patients who ALT values increased >6X ULN, the ALT will be monitored daily with a study CMP until the values are no longer increasing, then once weekly or until patient is clinically stable for discharge, whichever is first.

ACS severity definition

ACS is defined as a new pulmonary infiltrate associated with fever, chest pain or respiratory symptoms. ACS is a clinical diagnosis and will be determined based on discharge diagnosis by the hematology team. Severity of ACS for the purposes of this study will be defined as mild, moderate or severe based on the

criteria below, based on a definition created for other trials in SCD.

- **Mild:** +CXR with no oxygen use or transfusion required
- **Moderate:** +CXR associated with oxygen use or rbc transfusion
- **Severe:** +CXR and PICU transfer, intubation, and/or death

Study Compensation

Each consent participant will receive \$30 after randomization and completion of at least 1 study drug infusion and a second \$30 if they complete the discharge study requirements. Patients that do not complete the entire study will be paid for the days they have completed. Each participant will receive a total of \$60, if all study requirements are completed.

STATISTICAL ANALYSIS

Over a 1-year period, >1400 visits to CHOA EDs were recorded for children with SCD presenting for acute management of VOE. Over 500 of these visits through 2012 occurred between the hours of 7am and 3pm. Therefore, there is more than sufficient access to an eligible patient population due to the large volume of patients receiving care at the Aflac sickle cell center and its associated pediatric emergency departments.

The primary goal of this analysis is to compare the standard arginine treatment with placebo. The power analysis is based on this comparison. This sample size calculation is based on a two-sample two-sided t-test, with the objective of detecting a 55% reduction in opioid use from its mean value (4.1) in the placebo group based on the preliminary data generated from the recent [name] arginine trial (1). Based on these findings, the standard deviations are 2.0 and 4.1 (days) in the arginine and the placebo groups, respectively. A sample size of 33 subjects per group has 80% power to detect the treatment effect stated above on a two-sided test at the 0.05 significance level. A secondary goal is to compare the other arginine treatment arm (with a loading dose) to the placebo arm. Finally the two arginine treatments will be compared to determine if there is any difference or trend towards a difference when a loading dose is used that is superior to the standard arginine dose used with success in prior studies. Based on past experiences with arginine therapy, few patients withdrew from the study after the therapy was switched from oral to parenteral. Up to 150 patients will be enrolled, allowing for screen failures and study withdrawal, in order to insure randomization and study completion of 108 patients (36 per group) allowing for a 7% withdrawal rate. We did not adjust the sample size calculations for multiple comparisons as the power calculation only corresponds to the primary goal involving a single comparison of patients receiving the standard treatment or the placebo. We anticipate that the "loading dose" arm will be either the same or better than the standard dose. We will evaluate the efficacy and safety of this loading dose compared to the placebo group.

Each of the comparisons mentioned above will be conducted via a general linear model analysis. Predictors will include the treatment indicator, use of HU, age group, gender and the interactions of each of the last three covariates with the treatment indicator. By including interactions in the model we will be able to determine whether the treatment effect varies across subgroups of patients.

Assistance with statistical analysis and power calculation was provided by the Department of Biostatistics and Bioinformatics at the Rollins School of Public Health, Emory University, by [name] PhD, who will be the biostatistical consultant on this project.

Sample size power analysis for LOS as outcome: Goal for a future phase 3 RCT

This proposal will help provide more accurate data to generate a sample size power analysis for decreased LOS as the primary outcome measure in a multi-center Phase 3 RCT in the future.

If the true difference (based on the [name] et al (1)) between groups were 17 hours for LOS, n=150 subjects would be required in each group to have 80% power to detect a difference, assuming a 5% type 1 error rate and estimated standard deviation of ~ 50 hours. Given > 20 hour delay in administration of study drug from time from ED presentation for most patients in the [name] study (1), study drug administration within < 12 hours of ED presentation (ideally < 4 hours) will improve our power to detect a difference in LOS, likely requiring a smaller sample size. See below calculations and **Figure 11**. If the true decrease in LOS were closer to 24 hours (theoretically achievable with the elimination of delay in study drug delivery), a sample size of 76 patients in each group (n=152 total) is needed, approximately half the size required based on our current data. This proposed study is therefore a sound investment to insure the best design for a future phase 3 trial that will advance this orphan drug towards FDA regulatory approval.

Two-Sample T-Test Power Analysis

Numeric Results for Two-Sample T-Test

Null Hypothesis: Mean1=Mean2. Alternative Hypothesis: Mean1≠Mean2

The standard deviations were assumed to be unknown and unequal.

Allocation									
Power	N1	N2	Ratio	Alpha	Beta	Mean1	Mean2	S1	S2
0.80251	150	150	1.000	0.05000	0.19749	0.0	17.0	43.0	60.0
0.80277	134	134	1.000	0.05000	0.19723	0.0	18.0	43.0	60.0
0.80154	120	120	1.000	0.05000	0.19846	0.0	19.0	43.0	60.0
0.80007	108	108	1.000	0.05000	0.19993	0.0	20.0	43.0	60.0
0.80385	99	99	1.000	0.05000	0.19615	0.0	21.0	43.0	60.0
0.80254	90	90	1.000	0.05000	0.19746	0.0	22.0	43.0	60.0
0.80045	82	82	1.000	0.05000	0.19955	0.0	23.0	43.0	60.0
0.80361	76	76	1.000	0.05000	0.19639	0.0	24.0	43.0	60.0

Power Analysis Summary Statements

Group sample sizes of 150 and 150 achieve 80% power to detect a difference of -17.0 between the null hypothesis that both group means are 0.0 and the alternative hypothesis that the mean of group 2 is 17.0 with estimated group standard deviations of 43.0 and 60.0 and with a significance level (alpha) of 0.05000 using a two-sided two-sample t-test.

Site Monitoring Plan

The study coordinator will notify the Principle Investigator (PI) of all adverse effects. The PI will review the Adverse and Serious Adverse Event reports within 24 hours of being reported. All Serious Event Reports linked to study drug will be submitted to the FDA within the required time frame and the IRB will be notified per protocol. Summaries of all Adverse Event Reports will be provided to the FDA quarterly and IRB annually. After the occurrence of 2 Serious Adverse Events related to study medication, the study will be halted until a modification in design can be considered and submitted for IRB and DSMB PCRC Advisory board approval before continuing the study.

Data Safety Monitoring Plan

An Independent Data Safety Monitoring board, which is a group of experts not connected to the study, will be reviewing the data from this research throughout the study. Participants will be informed about new information from this or other studies that may affect their health, welfare, or willingness to stay in the study. The study Principle Investigator (PI) will review the Adverse and Serious Adverse Event reports within 24 hours. All Serious Event Reports linked to study drug will be submitted to the FDA within 24 hours and the IRB will be notified per protocol. Summaries of all Adverse Event Reports will be provided to the FDA quarterly, and IRB annually. After the occurrence of 2 Serious Adverse Events related to study medication, the study will be halted until a modification in design can be considered and submitted for IRB and DSMB Advisory board approval before continuing the study. A Data Safety Monitoring Board will be established from individuals not involved in this project, consisting of 1 pediatric hematologists from the Aflac Sickle Cell Center, one pediatric emergency medicine physician from Children's Healthcare of Atlanta, one individual with SCD expertise and past DSMB experience from outside Emory, and one biostatistician to be identified from the Data Coordinating Center. Drs. [name] [name], Director of Hematology, Aflac Cancer and Blood Disorders Center, Emory University School of Medicine, [name] MD, MBA, Marcus Professor and Vice Chair, Department of Pediatrics, Emory University School of Medicine, and [name] MD, Associate Professor of Medicine, Director of the Pulmonary Hypertension Program, Boston Medical Center, Boson University School of Medicine, have all committed to participation in the DSMB. The DCC biostatistician will be [name] MPH from the Emory Department of Pediatrics. The arginine arms of this study will be performed under an active IND for arginine therapy in sickle cell disease held by [name] amended to reflect this study design.

Adverse Events

Adverse Event Definition

As defined by the International Conference on Harmonization (ICH) E-6 Guidelines for Good Clinical Practice, an adverse event is any untoward medical occurrence in a subject administered an investigational product and that does not necessarily have a causal relationship with this treatment. An AE can therefore be any unfavorable and unintended sign (including an abnormal laboratory finding), symptom, or disease temporally associated with the use of an investigational product, whether or not related to the investigational treatment.

In this study collection of adverse events will begin at the time informed consent is obtained in the ED at the time they present for a pain crisis.

Pre-existing conditions which worsen during a study are to be reported as AEs.

Adverse Event Assessment

Adverse events should be assessed for intensity, relationship to the investigational product, expectedness, and seriousness. The investigator team is responsible for the assessment of all adverse events. During the clinical trial all adverse events will be reported on the AE eCRF.

Intensity

Intensity will be graded as mild, moderate, severe, or life-threatening as defined below:

- Mild: Discomfort noticed but no disruption of normal daily activity
- Moderate: Discomfort such that normal daily activity is affected
- Severe: Inability to work or perform normal daily activity

- Life Threatening: Represents an immediate threat to life

The term severe relates to the intensity of the adverse event. An event may be assessed as “severe” but not meet the criteria for a Serious Adverse Event as outlined in Section on Seriousness, below.

Relationship to Study Treatment / Procedures

Relationship to investigational product refers to the cause of the event and will be assessed using the following scale:

- Definitely Related: Event clearly related to investigational product.
- Probably Related: Event is likely to be related to the investigational product.
- Possibly Related: Event is unlikely or doubtful to be related to the investigational product.
- Not Related: Clearly not related to the investigational product.

Expectedness of Adverse Event

All adverse events will be evaluated as to whether their occurrence was expected (anticipated) or unexpected (unanticipated).

Unexpected:

An unexpected adverse event or adverse treatment reaction is one for which the nature or intensity is not consistent with either:

- Known information associated with the procedures and described in the protocol, consent form, or product brochure, and other relevant sources of information, or
- The expected natural progression of any underlying disease, disorder, or condition of the subject(s) experiencing the adverse event and the subject's predisposing risk factor profile for the adverse event.

Expected:

An event is considered expected if it is known to be associated with the study treatment or the expected natural progression of the subjects' underlying disease or condition.

Expected events related to opioid administration include the following:

Table 1. Expected Adverse Events Related to Opioid Administration

Anorexia	Headache
Apnea	Hypotension
Biliary tract pressure	Miosis
Blurred vision	Nausea
Bradycardia	Palpitations
Bruising	Pruritus
Cardiac arrest	Rash
Confusion	Respiratory arrest
Cramps	Respiratory depression
Diaphoresis	Sedation
Diplopia	Shock
Dizziness	Tinnitus

Drowsiness	Urinary retention
Euphoria	Urticaria
Flushing	Vomiting

Expected events related to sickle cell disease progression include the following:

Table 2. Expected Adverse Events Related to Sickle Cell Disease Progression

Acute chest syndrome	Jaundice
Angioedema	Leukocytosis
Aplastic crisis	Meningitis
Aplastic crisis/anemia	Metabolic acidosis
Arthralgia	Osteomyelitis
Appendicitis	Pyleonephritis
Bone Infarction	Pain, joint
Cardiomegaly	Pain, long bone
Cerebrovascular accident	Pain, severe abdominal
Cholecystitis, hepatic sequestration	Priapism
Cranial nerve palsy	Pulmonary embolism
Decreased kidney function	Pulmonary hypertension
Decreased lung function	Pulmonary parenchymal infiltrates on CXR
Delayed growth/puberty	Pneumonia
Depresses ESR	Rhabdomyolysis
Fever	Renal Failure
Headache	Renal Insufficiency/albuminuria
Hematuria	Renal papillary necrosis
Hemiplegia	Reticulocytosis (10%-20%)
Hemolysis	Retinal disease
Hepato/splenomegaly	Retinal hemorrhage
Hyperplastic bone marrow	Skin ulcers
Hyposthenuria	Splenic sequestration
Hypoxia (PO ₂ < 85 mm Hg)	Stroke
Hyperkalemia	Sepsis
Hypotension	Upper respiratory infection
Infection, pneumococcal	Urinary tract infection

Seriousness

An adverse event is considered serious if it meets at least one of the following criteria:

- Results in death; (Note: Death is an outcome not an event).
- Is life-threatening (places the subject at immediate risk of death from the event as it occurred);
- Results in inpatient hospitalization or prolongation of existing hospitalization;
- Results in a persistent or significant disability/incapacity;
- Results in a congenital anomaly/birth defect; or
- Based upon appropriate medical judgment, is medically significant or requires intervention to prevent one of the outcomes listed above.

Adverse events meeting the SAE criteria listed above will be assessed as to intensity, relationship to the investigational product and expectedness as outlined in Section F.2.2.

Reporting of Serious Adverse Events

Any serious adverse event occurring within the course of the clinical trial related or probably related to study drug must be reported to the DCC within one working day of the investigator learning of the event. The investigator team is responsible for notifying the local Ethics Committee/IRB of a SAE in writing as soon as possible and in compliance with local and international laws and regulations.

This study adheres to the definition and reporting requirements of ICH Guidelines for Safety, Data Management, Definitions and Standards for Expedited Reporting, Topic E2. Complete information can be found in the Manual of Procedures.

Outcome of Adverse Events (AE)

Every AE must be followed to a definitive outcome or stabilization of the event, even when this requires a time period beyond the scope of the study (this is particularly applicable to serious adverse events (SAEs)).

Outcome is defined as information on recovery and any sequelae; what specific tests and/or treatment may have been required and their results. For a fatal outcome, cause of death and a comment on its possible relationship to the suspected reaction should be provided.

The terms used to define outcome are as follows (outcome of reaction/event at the time of last observation):

- **Ongoing**
- **Resolved without sequelae**
- **Resolved with sequelae**
- **Death**

Actions taken in response to an AE and follow-up results must be recorded in the subject's medical record (this includes follow-up laboratory results). Any treatment administered for the adverse event must be recorded in the subject's electronic case report form (eCRF). When subjects are discontinued from the study due to an AE, relevant clinical assessments and laboratory tests will be repeated as necessary until final resolution or stabilization occurs.

Post-Study Procedures for Adverse Events

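### The acidosis exclusion (CO₂ ≤ 16) is not enforced before the first dose for children cleared on a CMP up to 12 months old

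*Combined protocol and SAP*

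**What the plan says.** Four parts of the protocol bear on this.

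- **Exclusion Criteria.** The list includes "Acidosis with CO₂ ≤ 16", with no look-back period.
- **Randomization and Arginine/Placebo Administration, order of steps.** "Once written informed consent is obtained, and eligibility is confirmed by study staff, children and adolescents age 3-21 years will be randomized". Two branches then depend on the past 12 months of laboratory results.
  - *Hold branch:* if there is no measurement in that period, or "if either SGPT/ALT or creatinine were elevated in the past 12 months (meeting exclusion criteria), the current CMP results must be reviewed" before dosing. Randomisation need not wait: "Patient may be randomized; however, delivery of study drug should be held until CMP results are reviewed and no exclusion criteria are noted".
  - *Dose-first branch:* if the past results met no exclusion criterion, "the patient can receive the first dose of study drug and the CMP and creatinine labs reviewed when available".
- **Same section, safeguard.** "Patients with a CMP after randomization that meet exclusion criteria will have study drug stopped for toxicity monitoring". No deadline for reading the result is given.
- **Toxicity Monitoring/ Study Drug Stopping Rules.** CO₂ ≤ 16 appears again, as a reason to end study drug.

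The laboratory schedule under Monitoring During Study places a CMP on Day 0, and its footnote puts Day 0 before study drug. The sample therefore exists before the first dose; the dose-first branch simply does not require anyone to look at it.

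**The concern.** The hold branch is triggered by a missing panel or by past ALT or creatinine. CO₂ is not a named trigger. A child can have had an acceptable CO₂ months ago, be acidotic now, and receive study drug while the result that would exclude the child is pending.

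This matters for this product in particular. The background section giving the rationale for a loading dose notes that the hydrochloride salt can induce acidosis. Table 2 lists metabolic acidosis among the events expected from sickle cell disease itself, so it can be present before any study drug. In the loading arm the dose given with the panel unread is the largest single dose in the trial. What is at stake is an entry criterion in a paediatric trial that the dosing rule bypasses.

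**Working it through.** The plan gives no figure for this point, so the check is mainly a comparison of texts, followed by small calculations of exposure, frequency and delay.

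**1. Can the look-back serve CO₂ as it serves ALT and creatinine?** Compare entry limits (Exclusion Criteria) with stopping limits (Toxicity Monitoring).

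| Measure | Excluded at entry | Drug stopped later |
|---|---|---|
| ALT | > 3 × upper value | > 6 × ULN |
| Creatinine | > 1.0 | > 3 × entry value, or > 2.0 |
| CO₂ | ≤ 16 | ≤ 16 |

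A child slightly over the ALT or creatinine entry limit is still below the toxicity limit. CO₂ has no such margin: any child dosed in breach of the exclusion meets a toxicity stopping rule at that dose.

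**2. Does another clause close the gap?** Eligibility is to be confirmed before randomisation, but the dose-first branch expressly lets the current panel wait, so that confirmation need not include a current CO₂. The later stop acts only after the result is read, which may be after a dose.

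**3. Exposure.** The dose-first permission covers the first dose only.
- Standard arm: 100 mg/kg. Loading arm: 200 mg/kg. Placebo arm: saline.
- The load relative to the 500 mg/kg single dose that the study drug infusion text reports as tolerated in sickle cell disease: 200/500 = 40%.

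**4. Frequency.** The documents give no rate of CO₂ ≤ 16 at presentation. As an assumption, take 1% to 5%, with every child dosed before the panel is read.
- Both arginine arms, 2 × 38 = 76 children: 76 × 0.01 = 0.76 to 76 × 0.05 = 3.8.
- Loading arm alone: 38 × 0.01 = 0.38 to 38 × 0.05 = 1.9.

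**5. Effect on the primary comparison.** The plan's sample size is reproduced first. Difference 0.55 × 4.1 = 2.255; SDs 2.0 and 4.1, so the summed variance is 4.00 + 16.81 = 20.81. By the normal approximation, n = (1.960 + 0.842)² × 20.81 / 2.255² ≈ 32.1, rounded up to the plan's 33 per group. An unequal-variance t calculation gives 79.4% power at 33.

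Now suppose a fraction f of the standard arm is stopped after one dose and gets no benefit at all, so the difference shrinks to 2.255 × (1 − f). At the 36 completers per group in the Statistical Analysis section:
- f = 0: 82.9%
- f = 1%: 82.1%
- f = 5%: 78.9%

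The loss is 0.8 to 4.0 percentage points, and the upper end takes the worst case on every input.

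**6. Delay if CO₂ is read first.** Laboratory turnaround is not given; 1 to 4 hours is assumed.
- Against the 2–4 hour ideal goal in Specific Aim 1: 1/4 = 25% to 4/2 = 200%.
- Against the 24-hour limit for randomisation: 1/24 = 4% to 4/24 = 17%.

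**The case against.** The best defence is that the two branches are a deliberate trade-off. The case for a loading dose rests on early delivery, and the plan aims for study drug within 2–4 hours. Children with no recent panel or a past abnormality are held, the rest are dosed, and drug is stopped on a bad result. Altered mental status, treated hypotension, PICU admission from the ED and investigator judgement also exclude, so a visibly ill child can be kept out without a CO₂ value. The protocol regards a one-time load as safe and ties its acidosis worry to higher doses over time.

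Much of this stands. It shows that the look-back was intended and that the risk per child is limited. It does not show that an old CO₂ can do the job of a current one, and the tolerance data do not address children who are already acidotic. Nor is a current-visit check foreign to the design: the pregnancy test must come from enrolment or from within 24 hours of randomisation.

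Two further objections deserve weight.

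- **No passage says that CO₂ comes with the CMP.** If it came from another test, the eligibility confirmation before randomisation would apply and there would be no gap.
- **Treating CO₂ as more acute than ALT or creatinine is a clinical judgement, not a statement in the plan.** The clause quoted under the safeguard stops drug for any exclusion result, ALT and creatinine included. The identical entry and stopping limits for CO₂ are nevertheless the protocol's own.

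A reader might infer from the missing deadline that two or three doses could be given unread, up to 400 mg/kg in the loading arm at 8-hour spacing. The documents do not support this: only the first dose is permitted before review. The silence on timing is an ambiguity worth closing, not an authorisation.

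**Conclusion.** The point holds in a limited form. On the dose-first track, the CO₂ exclusion is not enforced before the first dose, so a child whom the protocol means to exclude can receive one dose of study drug. This rests on the assumption that CO₂ is reported with the CMP.

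The number of such children is unknown and could be zero. Harm is not shown. The consequence is for safety and the integrity of eligibility; the efficacy analysis is barely affected.

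Two stronger readings should be resisted. One is that the 12-month look-back is unsound as a whole; for ALT and creatinine it is a defensible choice that this point does not dispute. The other is that the primary outcome becomes undefined. A child dosed first has a start time for opioid counting. The difficulty arises only for children randomised and never dosed, whom the plan keeps ("With an intention-to-treat analysis, these patients will remain on study"), and it already exists under the ALT and creatinine hold. That handling, and whether a low pre-dose CO₂ found later is labelled a deviation or a toxicity stop, are separate clarifications.

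**What to change.** Keep the 12-month look-back for ALT and creatinine. For CO₂, require a value above 16 from the current visit before the first dose, taken from the Day 0 CMP or any faster result from the same visit.

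The better place for the check is the eligibility confirmation, before randomisation. A pre-dose check would meet the safety need. Checking earlier also makes an acidotic child a screen failure and not a randomised, undosed patient, and the exclusion list already keeps such a child eligible for a later episode: "Previous randomization in this arginine RCT (patient consented and screen failed before receiving study drug or placebo remains eligible for future participation".

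If the sponsor judges speed more important, the minimum change is one sentence stating that no second dose is given until the current CMP has been read.

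The cost is wording and some time. No extra blood draw is needed. A wait before randomisation cannot differ by arm, and it may overlap with consent, though the documents do not say. The wait can consume much or all of the 2–4 hour goal, and if CO₂ is available only from the CMP, the dose-first track is largely given up. A faster source of CO₂ would avoid most of that loss.
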